3.2.1. Blinding

The subject, sponsor, and hypertensionist/nephrologist performing the screening and follow-up assessments are blinded. The interventionalist and cath lab staff are unblinded. Details of study blinding are contained in the study Randomization and Blinding Plan.

3.3. Description of Study Hypotheses

This study is designed as a proof-of-concept study. It is therefore not formally powered for the primary endpoint. The purpose of the trial is to determine if there is an adequate treatment effect to proceed to a pivotal study. It is planned to randomize approximately 90 subjects (45 per group) to achieve 80 evaluable subjects (for the primary efficacy endpoint analysis).

Primary Efficacy Endpoint

The primary efficacy endpoint of the change in mean 24-hour ambulatory SBP at 8 weeks post-treatment will be compared between the 2 treatment groups.

The following table provides examples of observed treatment effects and standard deviations (SDs) that would be considered statistically significant at alpha = 0.05, for the change in mean 24-hour ambulatory SBP at 8 weeks post-treatment with 80 evaluable subjects:

Treatment Difference	Standard Deviation
3.5 mmHg	8 mmHg
4.4 mmHg	10 mmHg
5.3 mmHg	12 mmHg

A study of the planned size would be powered at 80% to detect a difference between intervention and control of 5.1 mmHg assuming a SD of 8 mmHg in each group and two-sided alpha of 0.05 using the independent two-sample t-test. A difference between treatment and control of 5 mmHg is considered clinically meaningful and consistent with previous trials of renal denervation in a similar population (Townsend et al. 2017). An observed difference between groups of 5 mmHg with an observed SD as high as 11.2 mmHg per group would be considered statistically significant at a two-sided alpha level of 0.05.

3.4. Study Endpoints

3.4.1. Primary Efficacy Endpoint

The primary efficacy endpoint is defined as the change in mean 24-hour ambulatory SBP from baseline to 8 weeks post-treatment. This will be summarized and compared between the 2 treatment groups using the independent two-sample t-test.

3.4.2. Secondary Efficacy Endpoints

Secondary efficacy endpoints include:

- Change in mean 24-hour ambulatory diastolic blood pressure (DBP) from baseline to 8 weeks
- Change in mean 24-hour ambulatory SBP and DBP from baseline to 6 months and 1 year
- Change in mean daytime (07:00 to 21:59) ambulatory SBP and DBP from baseline to 8 weeks, 6 months, and 1 year
- Change in mean nighttime (22:00 to 6:59) ambulatory SBP and DBP from baseline to 8 weeks, 6 months, and 1 year
- Change in mean office SBP and DBP from baseline to 8 weeks, 6 months, 1 year, and 2 years
- Percentage of subjects controlled to target blood pressure values.
- Use of antihypertensive medication(s) from time of procedure to 8 weeks post-treatment (emergency use medication).
- Use of antihypertensive medication(s) (including increases/decreases) from 8 weeks to 6 months post-treatment (titrated according to standardized formula to maintain a target office SBP of <140 mmHg and ≥90 mmHg, see Section 7.2.2 of the protocol for more detail regarding medication titration).
- Compliance with not taking antihypertensive medications, as assessed by blood and urine testing, through 8 weeks post-treatment.

3.4.3. Secondary Safety Endpoints Secondary safety endpoints include:

- Major adverse events (MAEs) through 30 days post-treatment, as adjudicated by the Clinical Events Committee (CEC). A MAE is defined as any of the following:
 - o All-cause death
 - o End-stage renal disease (ESRD) (eGFR <15 mL/min/1.73 m² or need for renal replacement therapy)
 - Significant embolic event resulting in end-organ damage or requiring intervention to prevent it
 - Major vascular complications, including major renal artery dissection, renal artery aneurysm or pseudoaneurysm that required intervention or led to renal artery stenosis (>60% diameter stenosis)
 - o Major bleeding related to renal denervation within the renal arteries, or related to the Peregrine Catheter when in the body (per protocol bleeding definition)
 - Significant acute (post-procedural) renal artery stenosis (>60% diameter stenosis) as indicated by the renal angiogram post renal denervation, and confirmed by the angiography core laboratory, which led to one of the following: (i) acute kidney injury per modified Risk, Injury, Failure, Loss of kidney function, and End-stage kidney disease (RIFLE) definition, as confirmed by renal function blood test, or (ii) percutaneous intervention.
 - Hypertensive crisis (hypertensive emergency only)

- Hypotensive crisis
- Symptomatic hypotension that required a change in antihypertensive medications, or medications to increase blood pressure (e.g., persistent syncope, lightheadedness)
- Changes in eGFR from baseline to 8 weeks and 6 months post-treatment.
- Decreases in eGFR >25% from baseline to 8 weeks and 6 months post-treatment.
- Rate of adverse events (AEs) (serious and non-serious), peri-procedurally, at discharge, and at each of the follow-up time points.
- Device success (defined as the ability to insert the Peregrine Catheter into the lumen of the renal artery [target vessel], deploy the guide tubes inside the renal artery, deploy the needles through the arterial wall, deliver the intended dose of alcohol, retract the needles and the guide tubes back in the catheter, and remove the catheter from the access site without any related complications or events)
- Procedure success (defined as device success with freedom from peri-procedural MAEs).

Adverse events will be recorded from the time of signing the informed consent form through the end of study participation. Date of report; date of onset; whether the AE is serious or not; whether the AE is considered an MAE; whether the AE is considered a serious adverse device effect (SADE); whether the AE is considered a suspected unexpected adverse drug reaction; causal relationship (to Peregrine Catheter, study drug [alcohol], and study procedure, separately); action taken; outcome; date recovered/resolved; and date of death (if applicable) of each adverse event will be recorded.

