clinically meaningful and consistent with previous trials of renal denervation in a similar population¹. An observed difference between groups of 5 mmHg with an observed SD as high as 11.2 mmHg per group would be considered statistically significant at a two-sided alpha level of 0.05.

Endpoints and Planned Statistical Analysis

The following populations are defined for analysis:

The Intent-to-Treat (ITT) Analysis Set will include all subjects who were randomized regardless of whether treatment was received. Subjects will be analyzed according to their randomized treatment group, irrespective of treatment received.

The Safety Analysis Set will include all subjects who received treatment. Subjects will be analyzed according to the actual treatment received, irrespective of treatment assignment.

The Per-Protocol (PP) Analysis Set will include subjects with no important protocol deviations. Subjects will be analyzed according to the actual treatment received.

Primary efficacy endpoint

The primary efficacy endpoint is defined as the change in mean 24-hour ambulatory SBP from baseline to 8 weeks post-treatment. This will be summarized and compared between the 2 treatment groups using the independent two-sample t-test.

Secondary efficacy endpoints:

- Change in mean 24-hour, daytime, (07:00 to 21:59), and nighttime (22:00 to 06:59) ambulatory SBP and DBP from baseline to time points post-treatment.
- Change in mean office SBP and DBP from baseline to time points post-treatment.
- Percentage of subjects controlled to target blood pressure values.
- Use of antihypertensive medication(s) from time of procedure to 8 weeks post-treatment (emergency use medication).
- Use of antihypertensive medication(s) (including increases/decreases) from 8 weeks to 6 months and 1-year post-treatment (titrated according to standardized formula to maintain a target SBP of <140 mmHg and ≥90 mmHg).
- Compliance with not taking antihypertensive medications through 8 weeks post-treatment.

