- 11 If the renal duplex ultrasound assessment at 6 months cannot be performed, or if the results are non-diagnostic, CTA/MRA/renal angiography may be performed if agreed with the sponsor (depending upon local regulatory approvals and site capacity). If renal artery stenosis of >60% or any other significant abnormality is suspected or confirmed by renal duplex ultrasound, as evaluated by the core laboratory, or as the result of other clinical assessments, those findings should be confirmed using the imaging modality used at screening (CTA/MRA/renal angiography). The choice of imaging may be changed at the discretion of the investigator and should be discussed with the sponsor.
- 12 Subjects with an eGFR of >45 and <60 mL/min/1.73 m² based on the screening serum creatinine sample will undergo blood sampling for post-contrast serum creatinine measurement 48-96 hours after imaging at screening. Subjects with an eGFR of >45 and <60 mL/min/1.73 m² based on the Week -1 (baseline) serum creatinine sample will undergo blood sampling for post-contrast serum creatinine measurement 48-96 hours after imaging during the procedure and any subsequent procedure where imaging contrast is used.
- 13 See Table 3 for details of blood and urine parameters. Tests to be done in the case of ET will be as for the Month 6 visit, but excluding compliance tests.
- 14 For measurement of serum creatinine only (all subjects). This sample must be taken prior to imaging at screening, because the eGFR value based on this measurement will be used to assess whether the subject is excluded or may proceed to have the screening imaging assessment.
- 15 Activated coagulation time (ACT) only is performed on Day 0, per the hospital's standard of care.
- 16 For compliance testing only.
- 17 No antihypertensive medications are permitted from the start of the run-in period until the subject has completed the visit at 8 weeks post-treatment (except in the case of emergencies).
- 18 Antihypertensive medications may be given after the 8-week visit if necessary (according to pre-defined criteria and proposed titration schedule).

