- 19 Screening visit: full physical examination, height, weight, temperature, and HR. Week -2: abbreviated physical examination, weight, temperature, and HR; Week -1: temperature and HR; Day 0: single measurement of cuff BP and HR before and after study procedure (while in cath lab/special procedure lab); Day 1: abbreviated physical examination, single measurement of cuff BP, HR, and temperature; Weeks 4 and 8, and Month 3: weight, HR, and temperature; Month 6: full physical examination, weight, HR, and temperature; Years 1 and 2: weight, HR, and temperature; ET visit: abbreviated physical examination, weight, temperature, and HR.
- 20 Subjects will record BP twice daily, any antihypertensive medication(s) taken, and other notes (e.g. symptoms, illnesses). Subjects do not have to complete the subject diary during the in-hospital period.
- 21 Randomization will be performed in the cath lab/special procedure lab after the subject has been sedated and after renal angiography.
- 22 Questionnaire to be conducted post-treatment (>4 hours and <24 hours).
- 23 All AEs must be recorded from the time of signing the informed consent form through the end of study participation.
- 24 All medications (prescribed or over-the-counter, including supplements) must be recorded from the time of signing the informed consent form through the 6-month follow-up visit (or time of early termination from the study, if prior to 6 months). All antihypertensive medications must be recorded starting from the time of signing the informed consent form through the 2-year follow-up visit (or time of early termination from the study). In addition, all medications (prescribed or over-the-counter, including supplements) taken within 14 days prior to the onset of a serious AE (SAE) or major AE (MAE), as well as during the SAE or MAE timeframe, must be recorded starting from the time of signing the informed consent form through the 2-year follow-up visit (or time of early termination from the study).
- 25 Crossover from the Sham Control Arm to the Treatment Arm may be allowed, at the discretion of the treating investigator, after the Data Safety Monitoring Board (DSMB) has reviewed the 1-year data from all subjects and the study has been unblinded.

Table 2 Schedule of Study Assessments (Crossover Phase)

Period	Re-Screening Period	In-Hospital Period		Follow-Up Period			ET ¹
Visit Time Point	Up to Wk -4	D 0 ²	D 1	D 2 to D 4 (48-96 h) ³	Wk 4	Mth 6	
Visit Window					+/-7 D	+/-4 Wk	

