5.4.1. Primary Efficacy Endpoint

The mean change in 24-hour ambulatory SBP from baseline to 8 weeks post-treatment will be presented in each group. The difference between groups will be summarized and compared using ANCOVA with adjustment for the baseline 24-hour ambulatory SBP.

The protocol defined window for the 8-week (56 day) visit is ± 7 days. For the purposes of analysis, measurements obtained within -15 days or ± 30 days (i.e., between 41 and 86 days) will be considered valid and will be analyzed as part of the primary endpoint analysis, provided that the subject remained off antihypertensive medication prior to collection of ABPM.

For the primary analysis, all available data will be used. There will be no imputation of data at 8 weeks. This analysis will be repeated in the PP analysis set.

In addition to the primary analysis, the following secondary and sensitivity analyses will be conducted:

- 1. Subjects who meet the protocol defined criteria for antihypertensive drug treatment and receive treatment within the 8 weeks prior to assessment of the primary endpoint will have their 8-week value imputed with their baseline value of ABPM.
- 2. Subjects who meet the protocol defined criteria for antihypertensive drug treatment and receive treatment within 8 weeks will be removed from the analysis.
- 3. Subjects who receive antihypertensive treatment within 8 weeks for any reason or in whom antihypertensive medications are detected via compliance samples will be removed from the analysis.
- 4. Missing data at 8 weeks will be imputed via multiple imputation techniques. The following covariates will be considered for the imputation: treatment group, age, gender, history of diabetes, BMI, anatomy defined by length from ostium to bifurcation, number of medications at baseline, baseline office systolic pressure, 8-week office systolic pressure, baseline 24-hour ambulatory SBP. These factors were chosen based on clinical experience and recent literature (Fengler, 2016) (Id, 2016) (Kandzari, 2015).
- 5. Missing data at 8 weeks and data for those subjects who meet the protocol defined criteria for antihypertensive drug treatment and receive treatment within 8 weeks will be imputed via multiple imputation techniques.

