6 (if needed)	Spironolactone or beta-blocker or clonidine	6
7 (if needed)	Spironolactone or beta-blocker or clonidine	7
8 (if needed)	Spironolactone or beta-blocker or clonidine	8

Abbreviations: ACE = angiotensin-converting enzyme; ARB = angiotensin receptor blocker; BP = blood pressure; CCB = calcium channel blocker; SBP = systolic blood pressure.

- 1. There will usually be 2 to 3 weeks between steps. If the target is reached, there are no further steps even if BP fluctuates above the target. If initial systolic blood pressure (SBP) is ≥160 mmHg, Steps 1 and 2 can be combined. Fixed-combination drug products can be used to decrease pill burden.
- 2. The treatment score will be used for the purpose of the statistical analysis.

Source: Weber et al. 2015

5.5.2.5. Use of Antihypertensive Medication(s) (including Increases/Decreases) from 8 weeks to 6 months Post-Treatment (Titrated According to Standardized Formula to Maintain a Target SBP of <140 mmHg and ≥90 mmHg).

The mean change in the number of antihypertensive medications will be summarized as described in Section 5.7 along with 95% CIs for the mean change in number of medications. The addition of new antihypertensive drugs will be considered an intensification of the antihypertensive regimen. Discontinuation of one or more of the baseline antihypertensive medications without an increase in dose of remaining drugs or addition of new drugs will be considered a reduction in antihypertensive drug regimen.

The mean treatment score will be reported by treatment group and the groups compared via Fisher's Exact test. These analyses will be conducted in the ITT and PP analysis sets.

5.5.2.6. Compliance with Not Taking Antihypertensive Medications Through 8 weeks Post-Treatment. The number and percent of patients in whom no antihypertensive medications are detected according to urine compliance results will be summarized by treatment group and compared using Fisher's Exact test. Subjects who meet the protocol defined criteria for antihypertensive drug treatment and receive treatment within 8 weeks will be excluded from the analysis. These analyses will be conducted in the ITT and PP analysis sets.

5.5.2.7. Use of Antihypertensive Medication(s) according to Defined Daily Dose.

In addition to the protocol specified analyses as described above, prescribed medications will be summarized according to the sum of the defined daily dose (DDD) in order to assess and

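### In the ITT compliance analysis, a subject with recorded antihypertensive intake outside the protocol criteria but negative urine, or with a positive blood test but negative urine, is counted as compliant

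*SAP*

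**What the plan says.** SAP 3.4.2 lists as a secondary efficacy endpoint "Compliance with not taking antihypertensive medications, as assessed by blood and urine testing, through 8 weeks post-treatment". The protocol synopsis has the same endpoint without naming a method: "Compliance with not taking antihypertensive medications through 8 weeks post-treatment".

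The analysis in SAP 5.5.2.6 is narrower than SAP 3.4.2: "The number and percent of patients in whom no antihypertensive medications are detected according to urine compliance results will be summarized by treatment group". The arms are compared by Fisher's exact test in the ITT and PP sets. There is one exclusion: "Subjects who meet the protocol defined criteria for antihypertensive drug treatment and receive treatment within 8 weeks will be excluded from the analysis".

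Protocol Table 3 schedules blood and urine compliance tests at Week -1, Week 4, Week 8 and Month 6. Table 1 footnote 16 marks the Week 4 samples "For compliance testing only". Two other sources record intake over the same weeks: the subject diary (Table 1 footnote 20, not completed in hospital) and the medication record, which must hold all antihypertensives from consent to 2 years (footnote 24).

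Elsewhere the SAP uses a broader rule. Item 3 of the sensitivity analyses in SAP 5.4.1 removes "Subjects who receive antihypertensive treatment within 8 weeks for any reason or in whom antihypertensive medications are detected via compliance samples". SAP 4.1 makes antihypertensive treatment before the primary ABPM an important deviation, so a recorded user leaves the PP set.

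**The concern.** The endpoint describes a period, from the procedure to Week 8. The classification rests on urine at two scheduled visits, and an assay sees only recent dosing. The trial records intake over the whole period, but SAP 5.5.2.6 uses that record only to exclude subjects treated under the protocol criteria. A subject who took a drug outside those criteria stays in the ITT denominator and, with negative urine, counts as compliant.

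The compliance percentage is what a reader will use to judge whether the 8 weeks were in fact drug-free. If recorded users sit in its numerator, it says something that other parts of the same report contradict. The gap between blood and urine in SAP 3.4.2 and urine alone in SAP 5.5.2.6 adds a second route to the same error, and it needs no assumption about assays.

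**Working it through.** The plan states no figure for this endpoint, so there is none to reproduce. The main check is to follow each kind of subject through the three rules.

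| Within 8 weeks of the procedure | SAP 5.5.2.6 (ITT) | SAP 5.4.1 item 3 | PP set (SAP 4.1) |
|---|---|---|---|
| Met the criteria and was treated | excluded | removed | removed |
| Recorded intake outside the criteria, urine positive | not compliant | removed | removed |
| Recorded intake outside the criteria, all samples negative | **compliant** | removed | removed |
| No recorded intake, blood positive, urine negative | **compliant** | removed | not settled by the text |
| No recorded intake, nothing detected | compliant | kept | kept |

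The third row is the conflict between the compliance analysis and the rest of the SAP. The fourth arises because the blood result named in SAP 3.4.2 has no effect in SAP 5.5.2.6. The fifth is beyond the reach of any rule based on these data.

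Three further points are open in the text:
- SAP 5.5.2.6 does not say how the Week 4 and Week 8 results combine.
- It does not say how a missing sample is handled.
- It names the ITT and PP sets, but the table list in SAP section 9 shows only an ITT compliance table (14.2.10). The PP version, which would drop recorded users, is not listed.

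**Effect of one subject.** With 45 per arm randomized, one subject moved from non-compliant to compliant changes the arm's rate by 1/45 = 2.2 percentage points. With 40 in the denominator it is 1/40 = 2.5 points.

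**How much of the period the samples can see (illustration).** SAP 5.2.8 puts Week 4 at day 28 and Week 8 at day 56. The documents give no detection window, so I assume w = 1 to 7 days before each sample. Coverage is 2w/56: from 2/56 = 3.6% to 14/56 = 25%.

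For one daily course of L days, with its start equally likely on any day that keeps it within days 1 to 56, there are 57 − L possible start days. Of these, L + 2w − 1 are detected by a sample on day 28 or day 56.

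| Course | Detected, w = 1 | Detected, w = 7 | Missed by both samples |
|---|---|---|---|
| 3 days | 4/54 = 7% | 16/54 = 30% | 93% to 70% |
| 7 days | 8/50 = 16% | 20/50 = 40% | 84% to 60% |
| 14 days | 15/43 = 35% | 27/43 = 63% | 65% to 37% |

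These figures show why negative samples cannot stand in for the record. They do not estimate how many subjects are misclassified.

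**The case against.** The best defence is that this is meant to be an objective measure. SAP 3.4.2 names testing as the method, and SAP 5.5.2.6 reports subjects with nothing detected. Recorded use is a separate endpoint in the same list (SAP 5.5.2.4), with medication counts in SAP 5.7 and a by-patient listing. On this view, a subject who is assay-negative in one table and a recorded user in another reflects two measures, not a contradiction. That holds for an assay statistic labelled as such, and is a reason to keep the assay-only line. It does not hold for a line reported as compliance through 8 weeks, and it does not explain why the blood test is dropped.

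A reader might infer more than the documents support:
- **That any recorded intake can be scored as compliant.** It cannot: subjects who met the criteria and were treated are excluded, which itself needs treatment records, and the PP set removes recorded users. The problem is confined to the ITT analysis.
- **That the primary result is undermined.** It is not. Sensitivity analysis 3 and the PP analysis remove these subjects, and SAP 5.4.1 accepts 8-week readings in its widened window only if the subject stayed off drug. None of this depends on the compliance percentage.
- **That the miss probabilities measure the inflation of the rate.** They give the chance that the samples miss a course under an assumed window. The number of subjects with recorded, off-criteria, undetected intake is unknown and may be zero.
- **That the Fisher comparison is biased towards no difference.** This would need equal assay sensitivity in both arms and no false positives, and the excluded rescue-treated subjects may themselves differ by arm. The SAP calls these analyses supportive and says there is no formal hypothesis testing (5.2.1, 5.2.6).

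It is also fair to say that the SAP never uses the diary: no table or listing draws on it, so its data may not be in the database. A correction should rest first on the medication log.

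**Conclusion.** The point holds in a limited form. In the ITT analysis, SAP 5.5.2.6 counts as compliant two kinds of subject whom sensitivity analysis 3 treats as drug-exposed: those with recorded intake outside the protocol criteria and negative samples, and those positive in blood but negative in urine. The PP definition also removes the first kind. Both follow from the text alone and need no assumption about detection windows.

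The size cannot be stated, because the documents give no frequency for either kind. Each such subject raises the arm's compliance rate by about 2.2 to 2.5 percentage points. The endpoint is supportive; the primary analysis and the sample size do not change. The table shells are not in the available text and might contain footnotes that narrow the gap, but SAP 5.5.2.6 as written does not.

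**What to change.** In SAP 3.4.2 and 5.5.2.6, use one definition. A subject is non-compliant if either of these holds:
- any post-procedure blood or urine compliance sample through Week 8 is positive;
- the concomitant medication log (and the diary, where its data are captured) records antihypertensive intake outside the protocol-defined criteria between the procedure and the 8-week ABPM.

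Subjects treated under the criteria stay excluded, as now. This follows the rule of SAP 5.4.1 item 3, which counts treatment for any reason or detection in a sample. State how a subject with a missing Week 4 or Week 8 sample is classified, and reconcile the analysis sets in 5.5.2.6 with the table list. Keep the assay-only percentage as a separate descriptive line.

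The cost is a short change to the SAP text and one derived flag, built from a log and assays that are already collected. If diary data are used, a rule is needed for disagreements with the log. The reported compliance rate may be slightly less favourable. Intake that is neither recorded nor detected remains unseen.
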